5.4 Risks of nodulectomy

Nodulectomies are a standard procedure to treat onchocerciasis in endemic countries since current approved medications cannot kill the adult worms in nodules. Nodulectomies will be performed in an operating room under sterile conditions. Onchocercomata will be removed under local anesthesia by an experienced physician. There is a risk of blood loss or infection at the incision site however, careful sterile techniques should mitigate this risk. Subjects will be required to stay from normal work for 1 week after nodulectomy to facilitate wound healing and will be paid for their loss of earnings.

5.5 Conducting the trial during the Covid-19 pandemic

Potential Risks to Participants

Severe acute respiratory syndrome coronavirus 2 (SARS-CoV-2 also known as COVID-19) is a virus that was first reported in China in late December 2019, but has since spread to most countries in the world, including the presence of some cases in Ghana. COVID-19 is spread from person-to-person contact through respiratory droplets of an infected individual (eg. from coughing, sneezing, breathing). In the current clinical trial, patients will be in contact with other patients and staff during transport to the study site and during their stay at the health center for enrollment and follow-up exams.

Mitigation Procedures

The following measures will be put in place during the trial to prevent the transmission of SARS-CoV-2:

- The Research team will follow the Ghana Health Service Ethics Review Committee (GHS-ERC) Guidelines for conducting research during the COVID-19 pandemic
- Participants will be educated on the COVID-19 pandemic with the emphasis on how COVID-19 is now being transmitted from human to human, adequate protection by practicing good personal hygiene, maintaining physical distancing, hand washing with soap and running water, and the use sanitizers and wearing of facemasks.
- Participants will be triaged in their communities by asking whether they have symptoms of cough, catarrh, and/or fever and will also have their temperatures checked. All participants with suspected symptoms of COVID-19 will be referred to the Nkwanta South District COVID-19 team.

- Participants who leave the study site after a visit will be encouraged to share any covid-19 test that they have been made to take as soon as they do so and the results of the test as soon as they become available.
- Physical distancing will be maintained in project vehicles during transportation to and from participants' communities and participants will be required to wash their hands with soap and water, sanitise their hands with alcohol-based sanitisers and wear facemasks during all transportations.
- On arrival at the center, participants will be required to wash their hands with soap and running water and to sanitise their hands with alcohol based sanitisers.
- To ensure proper physical distancing, fewer participants will be housed in the center at one time (no more than 14 instead of 20).
- The researchers will follow all preventive protocols as advised by WHO and the national directives on COVID-19 including adequate protection by practicing good personal hygiene through regular hand washing with soap and running water, the use of sanitizers, protective gloves and wearing of facemasks. Social/physical distancing will be observed at all times.
- Staff and participants will wear facemasks in examination rooms. Hand sanitizer will be in the exam rooms, and staff will sanitize all instruments such as slit lamps and OCT that contact patient's skin after each examination.

5.6 Study Benefits

Benefits to Individuals

All participants in the study have onchocerciasis, and participants will benefit from the study treatments. Treatment with IDA may sterilize or kill adult worms better than treatment with the comparator regimen IVM/ALB. Participants will also benefit by having onchocercal nodules surgically removed. Drugs used in this study (ALB and IVM) are also active against intestinal nematode worms.

Public health benefit

If IDA is more effective for achieving sustained clearance of Mf than the comparator (IVM/ALB), this could lead to accelerated elimination of onchocerciasis in many areas in Africa. If IDA (after IVM pretreatment) is well tolerated in persons with onchocerciasis, this strategy might be used to accelerate LF elimination in Africa in areas with co-endemic LF and onchocerciasis even if the regimen is not effective for onchocerciasis. However, additional larger safety studies would be needed before I/IDA could be accepted as a MDA regimen for use in areas with onchocerciasis.

Cost to Subjects

There will be no cost to study participants, and study medications will be provided free of charge. All costs related to parasitological, ophthalmological and clinical monitoring and nodulectomies will be covered by the study. Study participants will be provided free transportation to Hohoe and back to their home communities, and they will be provided with food and accommodation in Hohoe. Participants will be visited and examined for follow-ups in their communities by the research team. All visits and examinations including wound dressings will be free to participants.

5.7 Study Compensation

Compensation for Loss of Earnings

Subjects will not be paid for participation in this study. Subjects will be compensated for the loss of earnings for the participating in the study. The compensation will be based on the number of days spent participating in protocol related activity at the village/clinic facility in Hohoe. For each day of participation, each participant will be compensated forty Ghana Cedis (GH₵ 40:00) per day. Minors participating in the study will be compensated at the same rate. Compensation will be paid at the end of enrollment and at the conclusion of each follow-up visit.

Compensation for Research Related Injuries

Commercial clinical trial insurance will be purchased for this study. In the event that a subject experiences an AE attributable to treatment, the project will help support any medical treatment and hospitalization required. Participants (or their families) will be compensated if any participant dies or is disabled because of participation in the study according to procedures followed for clinical research projects in Ghana.

The study will comply with Ghanaian government guidelines that require insurance to cover all participants, investigators and the institution in the clinical trial in case of damage to health due to participation in the clinical trial. The risk for the current trial is very low since the study medications are widely used and considered to be safe. The clinical evaluation procedures (skin snips, ophthalmological examinations, and nodulectomies) are standard of care, low risk procedures that are unlikely to damage health.

6 INSTRUCTIONS FOR SPECIMEN PREPARATION, HANDLING, AND STORAGE

6.1 Specimen and Sample Handling

Specimens will be tested in clinical laboratories at Kpassa (skin snips) and at the UHAS School of Public Health Research Centre in Hohoe, Ghana (blood, urine, skin snips). Onchocercal nodules will be fixed in preservative and processed for histology at a histology laboratory with CAP (College of American Pathologists) or an equivalent international certification.

Samples (serum, urine, skin snips, nodules) sent outside of Ghana for testing or storage will be completely de-identified (study ID number only). De-identified samples will be sent to Washington University in St. Louis and/or Case Western Reserve University (USA). Samples may be stored at one or more of these sites. These samples will be used for onchocerciasis related studies only.

6.2 Specimen Shipment

Nodule histology slides will be read in two independent sites. One site will be the DOLF project reference laboratory ([name] Lab) at the Washington University in St. Louis. Shipments of nodules and slides will comply with Ghanaian and United States federal rules and with IATA regulations. The [name] Lab at Washington University in St. Louis is located at [name], [name]. Samples will be stored for up to 35 years and then destroyed according to regulatory guidance.

7 SAFETY REPORTING AND SAFETY MONITORING

Most treatment related adverse events (cutaneous or ocular) result from the death of microfilariae in the skin and/or the eye are related to death of parasites and are not due to direct toxic effects of the drugs in humans. Other adverse events such as nausea and abdominal pain sometimes occur after treatment with IVM, ALB, or DEC. These may be related to local physical effects of the tablets or to effects of these drugs on intestinal worms. AEs related to death of *O. volvulus* Mf typically occur following the initial (first time) treatment when the burden of Mf in the skin and eye is greatest. These AEs typically start 1 or 2 days after treatment and they may occur up to 7 days after treatment. After treatment, participants will be assessed daily in the center for adverse events for 7 days before being discharged to their communities.

If participants develop severe AEs (grade 3, events that interfere with activities of daily living) or serious AEs for any reason after they return to the Kpassa area, they will be transported to Kpassa Health Centre, Nkwanta District Hospital, or UHAS School of Public Health Research Centre at Hohoe hospital for evaluation and management. SAEs will be reported to the Ghana Food and Drug Administration (FDA), UHAS Research Ethics Committee, Ghana Health Service Ethics Review Committee (GHS-ERC), to manufacturers of study medications, and to other institutional review boards per Good Clinical Practice (GCP) guidelines and timelines.

More detail on Safety Reporting can be found in the Safety Plan corresponding to this study.

7.1 Definitions

Adverse Events (AEs)

Adverse events (AEs) are any untoward medical occurrence in a clinical investigation participant who has received a study product intervention. AEs do not necessarily have to be causally related to treatment with the study product. An AE can, therefore, be any unfavorable and unintended symptom, sign (including an abnormal laboratory finding) or other disease temporally associated with the use of a study medicinal product, whether or not the AE is considered to be related to the study medicinal product.

An AE does not include:

- Medical or surgical procedures (e.g. surgery, tooth extraction, transfusion). The condition that leads to the procedure is an adverse event
- Pre-existing diseases or conditions or laboratory abnormalities present or detected prior to the screening visit that do not worsen.

Ocular Adverse Events (OAEs)

Ocular adverse events are adverse events in the Guide for Assigning Adverse Events, or any other adverse event pertaining to the eye resulting in symptomatic, visual or functional disturbance.

Serious Adverse Event (SAE)

Any adverse event that results in any of the following outcomes:

- Death
- Life-threatening (immediate risk of death)
- Inpatient hospitalization or prolongation of existing hospitalization
- Persistent or significant disability or incapacity
- Congenital anomaly/birth defect
- Important medical events that may not result in death, be life threatening, or require hospitalization may be considered a serious adverse event when, based upon appropriate medical judgment, they may jeopardize the participant and may require medical or surgical intervention to prevent one of the outcomes listed in this definition. Examples of such medical events include allergic bronchospasm requiring intensive treatment in an emergency room or at home, blood dyscrasias or convulsions that do not result in inpatient hospitalization, or the development of drug dependency or drug abuse.

Ocular SAEs

An ocular severe adverse event will be defined as:

- An AE causing severe visual loss, defined as a decrease in VA of > or = 6 lines compared with baseline VA or a decrease in VA to level of 6/60 or worse
- An AE requiring medical or surgical intervention to prevent permanent loss of vision;
- An AE associated with severe intraocular inflammation;
- Conjunctival or scleral necrosis
- Corneal Edema or persistent corneal erosion
- Retinal Detachment
- Retinal Hemorrhage
- Optic Atrophy
- Increased IOP > 15 mmHg from baseline

Unexpected

An adverse reaction, the nature or severity of which is not consistent with the applicable product information (e.g., Package Insert).

Expedited Safety Report

Documentation in appropriate form and format summarizing an SAE that meets expedited safety reporting criteria, submitted within the required reporting time frame of applicable regulatory authorities and/or institutional review boards (IRBs) or ERCs of participating countries.

7.2 Assessment of Adverse Events

Adverse event monitoring will be performed daily for 7 days following treatment with study medications. Participants will be kept at the *UHAS School of Public Health Research Centre* clinical facility at the Hohoe municipal Hospital for 7 days after treatment so that they can be

closely monitored for adverse events and provided care if needed. See Appendix C for a sample AE assessment form.

Adverse events will be defined using a modified Common Terminology Criteria for Adverse Events (CTCAE) grading table. Study ophthalmologists have added additional detail to the CTCAE tables for potential ocular adverse events related to this study (Appendix D).

Evaluations will be documented on the case report forms (either paper or entered directly into an electronic CRF using a smart telephone or tablet computer).

After 7 days participants will be returned to their homes. They will be instructed to contact the study village coordinators who are resident in their communities to inform the study investigators of any late adverse events and arrange transportation to the Kpassa Health Centre/Nkwanta District Hospital/ or *UHAS School of Public Health Research Centre* at Hohoe hospital medical care if required.

7.3 Serious Adverse Event (SAE) Assessment and Management

Project ophthalmologists will manage any significant ocular AEs with treatments such as topical or periocular injections of anti-inflammatory medications (e.g., steroids). Extra-ocular AEs such as Mazzotti reactions (fever with skin rash, pruritus, and malaise) will be managed by study personnel with medications such as anti-pyretics, anti-inflammatory drugs and anti-histamines, which are routine, approved medications and will be prescribed by the study clinician. Study participants with definite or suspected SAEs (any event \geq grade 3) will be referred to a physician or appropriate health care professional for evaluation. The physician will determine whether the event qualifies as a serious adverse event (SAE).

All SAEs will be reported to regulatory authorities and to the Ghana FDA within the stipulated timelimes (see Safety Plan). The report will specify whether the SAE was related, possibly related or unrelated to treatment and also specify whether the type of AE observed is unexpected based on the study drug's package insert. (See Appendix C for a sample SAE report form.)

All AEs and SAEs will be recorded in source documents. All AEs and SAEs will be recorded in the CRFs approved by GHS-ERC. SAEs and follow-up information will be reported to each IRB per their approved reporting policies.

7.4 Reporting of Pregnancy

Pregnancy is an exclusion criteria for this study. Although not AEs, pregnancies are reportable events. If a pregnant woman is inadvertently dosed, efforts will be made to follow-up and report the outcome of the pregnancy (e.g., healthy baby, miscarriage, etc.) Any pregnant woman inadvertently dosed who has a miscarriage or spontaneous abortion will be reported as an SAE. If a participant becomes pregnant after treatment they may remain in the study, but the study will not actively follow the outcome of the pregnancy. Pregnancy will be diagnosed by a urine human chorionic gonadotropin (urine HCG) test. If a pregnant woman is inadvertently dosed with study medications for either intervention arm, the baby delivered as a result of that pregnancy will be followed for one year after birth.

7.5 Data Safety Monitoring Board

A *Data Safety Monitoring Board* (DSMB) will be formed consisting of at least 4 experts including: at least 2 physicians, one of which is an ophthalmologist; as well as one statistician, and at least one scientist or physician who is knowledgeable in onchocerciasis and neglected tropical diseases. At least one member of the DSMB will be a Ghanaian scientist or physician. Study investigators will send safety reports to the DSMB at least monthly, and the DSMB will meet when the first 30 participants have been enrolled, at the midpoint of the study, and after the second stratum of participants is complete. Thereafter, meetings will take place quarterly until all participants have completed 3 month follow-ups. Ad hoc meetings will be held as needed and in the event that the PI or other study staff note safety concerns during enrollment. The DSMB will monitor the type and frequency of AEs and SAEs recorded by the teams and provide guidance to the PIs and the teams in the field. A draft of the DSMB charter is located in Appendix E. The final version of this charter will be submitted to all IRBs after members of the DSMB have confirmed their participation.

7.6 Interim Analyses

Data will be analyzed during the study for “go” or “no go” decisions for continuation of the study. Interim analyses will be performed after enrollment and 7 day follow-up is completed for participants in stratum 1 and then again at the end of stratum 2. A third interim analysis will be performed after the 3 month assessments have been completed for all participants. Among other things, the DSMB should consider whether severe AEs are significantly more common after IDA than after IVM/ALB treatment. The DSMB will review safety data on a regular basis, and they will review all severe or serious ocular AEs as and when they occur. The DSMB will consider stopping the study if one or more participant experiences a serious adverse event attributable to IDA treatment. At each review, the DSMB will make a “go” ahead with the study or “no go” decision based on their analyses and assessment.

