3 HYPOTHESES

1. Triple drug therapy with ivermectin, diethylcarbamazine and albendazole (IDA) (following ivermectin pretreatment) is more effective for killing or sterilizing adult female *O. volvulus* worms than ivermectin plus albendazole.
2. Triple drug therapy with ivermectin, diethylcarbamazine, and albendazole (following ivermectin pretreatment) is as safe as IVM/ALB alone in persons with onchocerciasis.

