4.7 Participant Treatment

At baseline, participants will be given ivermectin (150 $\mu\text{g}/\text{kg}$) pretreatment. This pretreatment will be provided the participants' villages near their homes following their consenting to participate in the study. *Please note, *all participants* will be treated with ivermectin at baseline to ensure that they have low skin and ocular Mf counts at the time of enrollment. (This treatment is *in addition to* the pretreatment with ivermectin given in the Part I study).

After the baseline treatment with ivermectin alone, participants will be randomly assigned to one of the following treatment arms (all oral medications)*:

I. Ivermectin 150 $\mu\text{g}/\text{kg}$ plus albendazole (400 mg)

II. IDA single oral dose

- a. Ivermectin, 150 $\mu\text{g}/\text{kg}$

- b. Diethylcarbamazine citrate, 6 mg/kg
- c. Albendazole, 400 mg

III. IDA three one time daily oral doses

- a. Ivermectin, 150 μ g/kg
- b. Diethylcarbamazine citrate, 6 mg/kg
- c. Albendazole, 400 mg

Randomized treatment to one of the three treatment arms will occur in cohorts of up to 20 individuals. This is based on the project's capacity for transport, examination, and housing of participants. Initial participants will be individuals who had zero Mf in the eyes six months after pre-treatment with IVM in Part I and zero Mf in the eyes at baseline for Part II. If IDA proves safe in all of these participants,(i.e. if there are no serious or severe adverse events in *any* participant in the first 7 days) the study will continue with participants who had Mf in the anterior chamber in either eye six months after IVM pre-treatment in the Part I study or at the baseline exams for this study. Study investigators will monitor the safety of the participants in each treatment cohort for 7 days before dosing the next cohort, and they will suspend the study if any treatment-related serious or severe adverse events occur. If SAEs are reported, the DSMB will be asked to review the cases and to implement study stopping and pausing guidelines if the SAEs are found to be related to study treatments.

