7.7 Procedures for Pausing the Trial

Upon review of the safety data from the trial, the DSMB will make decisions regarding the continuation of the trial. The DSMB will conduct an initial review after study drugs are distributed to approximately 10 participants in each treatment arm and consider halting or stopping the study if 1 or more participants in any treatment arm experiences an SAE by month 3 after treatment. The DSMB will pause to review data after any SAE then start again following the review and determination of the study’s safety. Because participants will be recruited as cohorts, safety evaluations will be held on an ongoing basis and include cumulative safety data of grade 1 and 2 AEs and specific case information for grade 3 and above.

The DSMB has been convened to look out for the safety of study participants; it has the right and responsibility to pause the study if any of the treatments is associated with an unacceptable frequency of serious or severe adverse events. The DSMB should consult with the study medical monitor and PI before making a final decision to suspend the study. If the DSMB recommends discontinuation or modification of the study, the Chair of the DSMB will meet or speak to the DOLF Project Team at the earliest opportunity to review the basis for the recommendation, and the DOLF Project team will notify the Principal Investigator. The DSMB will begin data review meetings after enrollment of participants in the investigational arms of this study.

The DSMB and IRB/ERCs have the authority to stop the study at any point. The study may also be terminated by regulatory bodies if there is significant violation of GCP that compromises the ability to achieve the primary study objective or compromises subject safety.

However, as DSMB members are not on site, it is appropriate that they get input from the medical monitor and PI before making stopping or pausing decisions. The DSMB Chair will communicate the decision to discontinue or modify the study with the DOLF Project Team and the DOLF Project Team will immediately notify the PI of the DSMB's decision. The DOLF Team is in a better position to communicate with the DSMB Chair (only 1 hour time zone difference, more reliable internet, etc.).

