8.2 Data Analysis Plan

Efficacy analysis for primary outcome

Because of the within subject correlation for the primary outcome (% fertile female worms), we will use a generalized linear mixed model approach (PROC GLIMMIX, SAS)⁴⁶. Generalized linear mixed models (GLMM) permit modeling of non-normal outcomes while accounting for correlation among observations within a group. In the present study, the primary outcome is binary (0=non-fertile female worm, 1=fertile female worm) and worms within a person are not independent. To model these data we will use a GLMM assuming a binomial distribution with a logit link function,

and person will be treated as a random effect. Further, while we do not anticipate an effect of village on our outcomes, if subjects within village are correlated the GLMM can be extended to account for this correlation. A two-sided P -value ≤ 0.05 is considered significant for these analyses.

Efficacy analysis for secondary outcomes

Similar to the analysis of the primary outcome, percentage of all adult worms that are viable will be analyzed using a GLMM. Percent of persons with zero MF at 18 months will be analyzed using a generalized linear model assuming a binomial distribution and a logit link function. The difference between pre and post treatment MF counts (% reduction) will be analyzed using a paired t-test and will be transformed as necessary to meet the assumptions of this analysis. A P -value of 0.05 will be considered significant for all secondary outcomes.

Safety

The primary safety analysis will focus on AEs with severity grade 3 or greater. Secondary analyses will separately consider all AEs and ocular AEs. AEs will be assessed daily for 7 days after treatment and 3 months after treatment. This will include general assessments and detailed ophthalmological examinations on day 7 and 3 months after treatment. AE rates and severity will be compared across the three treatment groups using logistic regression analysis; with Student's t -test will be used to assess differences for individual AEs. The data will also be examined using a generalized linear mixed model that as described below can model non-normal outcomes and examine correlations among the different events and how these change over time. In this model, we can also examine the impact of baseline Mf burdens prior to treatment and other potential risk factors (age, sex, location, etc.) on AEs.

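### Hypothesis 2 says IDA is no less safe than IVM/ALB, but section 8.2 plans only tests of difference, with no margin or interval, so no planned analysis can support it

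*Combined protocol and SAP*

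**What the plan says.** Section 3, hypothesis 2, holds that triple therapy after ivermectin pretreatment "is as safe as IVM/ALB alone in persons with onchocerciasis". No margin is attached.

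Section 8.2 sets the endpoint: "The primary safety analysis will focus on AEs with severity grade 3 or greater". It sets the method as follows: "AE rates and severity will be compared across the three treatment groups using logistic regression analysis". It adds t-tests for individual events and a generalized linear mixed model. It names no margin and no confidence interval for a difference between arms, and it does not say which logistic test statistic will be used.

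Section 7.6 says, as one consideration among several, that "the DSMB should consider whether severe AEs are significantly more common after IDA than after IVM/ALB treatment". No test, alpha level or boundary is given.

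Other rules need no significance test:
- Section 7.6: "The DSMB will consider stopping the study if one or more participant experiences a serious adverse event attributable to IDA treatment".
- Section 7.7: the DSMB is to "consider halting or stopping the study if 1 or more participants in any treatment arm experiences an SAE by month 3 after treatment". It may also pause the study if any treatment shows an unacceptable frequency of serious or severe events.
- Section 4.7 says of the investigators that "they will suspend the study if any treatment-related serious or severe adverse events occur". It opens the second stratum only if the first has had no serious or severe event within 7 days.

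Sections 2.3, 4, 5.6, 8.1 and 8.2 say, in various words, that the safety data are preliminary or exploratory, or that larger studies are needed.

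**The concern.** A test of difference can show that IDA is worse. It cannot show that IDA is as safe, because a non-significant P value arises both when the arms are alike and when the trial is too small to tell them apart. Hypothesis 2 therefore has no analysis behind it: a null result merely fails to contradict it.

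Safety is one of two primary objectives, and section 4 expects the data to justify or rule out a larger safety study. For that decision the useful result is how large an excess of severe events the data leave possible. The plan does not call for that figure in section 8.2 or among the DSMB's questions in 7.6.

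**Working it through.** **Inputs from the documents.** Minimum 61 per arm (8.1). Up to 300 participants, evenly randomized to three arms (4.1, 4.4), so at most 100 per arm. Endpoint: grade 3+ adverse events (8.2).

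**Inputs assumed.** The documents give no grade 3+ rate for IVM/ALB and no alpha for safety. Control rates of 1% and 5% and two-sided 0.05 are assumed.

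**The plan's own figure.** The only sample size is for efficacy. For 30% vs 15% fertile worms, two-sided 0.05 and 80% power, the usual two-proportion formula gives 121 worms per group. The design effect is 1 + 0.30 × (6 − 1) = 2.5, and 121 × 2.5 / 6 = 50.4, so 51 subjects, as stated. Then 51 × 1.2 = 61.2, the stated 61. Safety plays no part in this number.

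**What counts as significant.** Take 0 events on control and x on one IDA arm, 61 per arm.
- Fisher's exact test, x = 5: P = 2 × (61·60·59·58·57)/(122·121·120·119·118) = 0.057. For x = 6, multiply by 56/117: P = 0.027. So 6 events are needed. At 100 per arm 6 are also needed (P = 0.029).
- Likelihood-ratio test from logistic regression, x = 3: 2 × {[3 ln(3/61) + 58 ln(58/61)] − [3 ln(3/122) + 119 ln(119/122)]} = 2 × (−11.96 + 14.08) = 4.23, so P = 0.040. Three events are enough, and also at 100 per arm (P = 0.040).
- A Wald test does worse when an arm has no events, because the log odds ratio has no finite estimate.

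**Power.** This is the sum, over all pairs of counts with more events on IDA and P ≤ 0.05, of the product of the two binomial probabilities. The comparison is one IDA arm against control.

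| Assumed rates (control vs IDA) | 61 per arm: Fisher | 61 per arm: LR | 100 per arm: Fisher | 100 per arm: LR |
|---|---|---|---|---|
| 1% vs 3% | 1% | 15% | 3% | 24% |
| 1% vs 5% | 5% | 35% | 19% | 49% |
| 5% vs 15% | 33% | 50% | 59% | 68% |

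**What zero events would show.** The upper end of the exact two-sided 95% interval is 1 − 0.025^(1/n): 5.9% for n = 61 and 3.6% for n = 100. For both IDA arms pooled it is 3.0% (n = 122) and 1.8% (n = 200).

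**Would a margin do instead?** With equal true rates p, one-sided 0.025 and 80% power, the smallest margin that n per arm supports is about (1.96 + 0.84) × √(2p(1 − p)/n). At p = 1% this is 5.0 points for n = 61 and 3.9 for n = 100. A 2-point margin would need 389 per arm. The approximation is rough at such low rates, but a tight margin is out of reach, which points to estimation.

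**The case against.** A reader might infer that the DSMB's go/no-go decision rests on this significance question. It does not. Section 7.6 offers the question as one consideration among others, and the single-event rules in 4.7, 7.6 and 7.7 act whatever the P value. One severe event in the first stratum is enough to stop the second from opening. At a true 5% rate, the chance of at least one event among 122 IDA recipients is 1 − 0.95^122 = 99.8%, although suspension also requires the event to be judged treatment-related. The unacceptable-frequency standard in 7.7 needs no test either, and the DSMB sees case details for grade 3 and above. All of this stands. These rules protect participants and prompt review, but they do not estimate the difference between arms and so cannot support hypothesis 2.

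A reader might also infer that the trial is almost bound to find no significant difference. That depends on the test and on a control rate the documents do not state. At 5% vs 15% with 100 per arm, power is 59% to 68%.

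Finally, no section says that a non-significant result will be taken as safe or as a decision to continue, and the limits of the safety data are disclosed repeatedly. That is correct. The disclosure is what hypothesis 2 conflicts with. The DSMB charter and the Safety Plan, whose text is not available here, may hold further interim detail.

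**Conclusion.** The point holds as a mismatch between claim and method. Hypothesis 2 asserts that IDA is as safe as the comparator, section 8.2 contains nothing that could support this, and the plan elsewhere calls the safety part exploratory. Section 7.6 repeats the significance form for one of the DSMB's questions.

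A non-significant result would say little if severe events are rare on control: at 1% vs 5% a fivefold excess would be missed 65% to 95% of the time at 61 per arm, and 51% to 81% at 100 per arm. All of these rates are assumptions, and each range reflects the choice between a likelihood-ratio and a Fisher test. The zero-event limits of 5.9% and 3.6% depend only on arm size.

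The documents do not support saying that stopping decisions turn on significance, or that the investigators intend to report non-significance as safety.

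**What to change.** 1. Section 3: reword hypothesis 2 as estimation. The study will estimate the excess of grade 3+ adverse events after IDA over IVM/ALB and report the largest excess not excluded. State that P > 0.05 will not be reported as showing that IDA is as safe.
2. Section 8.2: add grade 3+ rates by arm and for the two IDA arms pooled, and the risk difference against IVM/ALB with a two-sided 95% exact or score interval.
3. Section 7.6: replace the significance question with DSMB review of these rates and intervals. Leave the single-event pausing rules unchanged.

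The cost is a few sentences and an extra table column, with no change to sample size or procedures. The safety conclusion that the trial may draw becomes more modest.
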